4.0	8 October 2021	
 a. Modified par. 2, 4 and 6 to align SPINERY intended purpose and clinical study objectives. b. Modified exclusion criteria n°10 in the Synopsis and in par. 6.3.2 c. Modified Table A - Schedule of Visits and in par. 6.4.3, added the control of Concomitant pain medication at 1 Month follow-up d. Added par. 6.3.3 “Vulnerable populations” e. Added in par. 6.4.4 “Concomitant pain medications” info related to evaluation of concomitant pain medications f. Correction of clerical error in par. 6.4.4 “Brief Pain Inventory - BPI” g. Modified par. 6.5 “End of Trial” specifying time and duty of the Sponsor h. Modified par. 8.1.1 “Adverse Event”, par. 8.1.2 Adverse Device Effect”, par. 8.1.4 “Severe Adverse Event”, par. 8.1.5 “Severe Adverse Device Effect”, added par. 8.1.3 “Unanticipated Adverse Device Effect”, par. 8.1.6 “Unanticipated Severe Adverse Effect” and par. 8.1.7 “Device Deficiency and Malfunction” i. Modified par. 8.2.2 “Reporting of a SAEs/ SADEs/ UADEs” to comply with national and european Regulations

		
 j. Modified par. 8.2.3 "Specific Adverse Device Effect" with indication to how minimize the risk of the study k. Modified Chapter 14 "Abbreviations" inserting OMED (Oral Morphine Equivalent Dose) l. Modified Chapter 15 "References" adding the following reference: "Patrick, D.L., Cleeland, C.S., von Moos, R. et al. Pain outcomes in patients with bone metastases from advanced cancer: assessment and management with bone-targeting agents. Support Care Cancer23, 1157–1168 (2015)"
5.0	1 December 2021	
 a. Added in Chapter 2 "Background and Rationale" more bibliography indications related to the the comparable efficacy of RF in pain reduction respect the standard therapy. b. Modified cap. 8.2.2 "Reporting of a SAEs/ SADEs/ UADEs" with correct indication of national regulations MDCG 2020-10/1 c. Added in Chapter 14 "Abbreviation" RT such as Radiotherapy d. Added in Chapter 15 "References" the new references mentioned in Chapter 2.

1. SYNOPSIS

Title	SPINERY A novel R adio- F requency T umor A blation D evice S tudy (SPARTA)
Reference number	Protocol #2020-01 (EU)
Sponsor	Axon srl [name]
Version and date	Version 7 of March 29 th , 2022
Investigational device	Axon SPINERY Radiofrequency Device with cooled bipolar and monopolar needles. SPINERY is a Radiofrequency (RF) device designed for local treatment of metastatic tumors localized in bone. The device is conceived to treat bone metastatic tumor areas using RF needles, with the aim of pain reduction. The RF needles are used single or in combinations to increase ablation efficacy. The SPINERY system consists in a RF generator connected to a 16G needle. The needles are bipolar or monopolar with cooling and equipped with two thermocouples (one distal to measure the center ablation temperature and one proximal to avoid hyperthermic damages to the healthy tissues. The procedure is conducted under Fluoroscopy imaging guidance.
Intended purpose	SPINERY is a Radiofrequency (RF) device designed for palliative treatment of patients with painful metastatic bone tumors involving vertebral bodies, sacrum, iliac crest and peri-acetabulum.
Intended clinical performance	SPINERY is a Radio-Frequency (RF) device designed for local treatments of metastatic bone tumors. In particular, SPINERY is conceived for: 
 • Pain reduction in patients affected by metastatic bone tumors involving the vertebral bodies, sacrum, iliac crest and peri-acetabulum, in patients with indication for Standard Therapy and in patients who have failed, not candidates or refuse Standard Therapy; • Coagulation and ablation of bone tissue during interventional procedures including palliation of pain associated with metastatic lesions involving bone also in patients who have failed, not candidates or refuse Standard Therapy.
Principal investigator(s)	[name]

	Azienda Ospedaliera di Rilievo Nazionale Antonio Cardarelli [name]
Investigation site(s)	All sites are listed in Annex 1.
External organizations	CRO Advice Pharma Group Srl Address [name]
Objectives and hypotheses	
Objective(s), primary and secondary	
Primary objectives:
 
 1. To demonstrate that SPINERY RF device is effective in short-term (3 months) pain reduction in patients affected by metastatic bone tumors involving the vertebral bodies, sacrum, iliac crest and peri-acetabulum with indication for standard therapy and in patients who have failed, not candidates or refuse standard therapy; 2. To demonstrate that SPINERY RF device is safe in the RF ablation treatment of metastatic bone tumors, without causing device-related adverse events including, in particular, nerve injury; 
Secondary objectives:
 
 1. To demonstrate that SPINERY RF device is effective in long-term (up to 12 months) pain reduction in patients affected by metastatic bone tumors in the areas of vertebral bodies (thoracic and/or lumbar), sacrum, iliac crest and peri-acetabulum; 2. To demonstrate safety in relation to usability; 3. To demonstrate the procedural performance in terms of a short learning curve.
Hypotheses, primary and secondary	
Primary hypothesis:
 
 - BPI Brief Pain Inventory scale performance in terms of palliative treatment: 
H0: $\mu_c = 0$
 
HA: $\mu_c \neq 0$
 
Where μ_c is the mean change from baseline to the 3-month visit in worst-pain score.
 
No formal hypotheses for the remaining objectives.

Risks and anticipated adverse device effects to be assessed	Risks of innovative device SPINERY are the same of the state-of-the-art technology: 
 - Carbonization - Post-operative pain

	
 - Limited/uncomplete treatment due to anatomical peculiarities - damage to surrounding tissue through iatrogenic injury - Nerve injury including thermal injury, puncture of spinal cord or nerve roots potentially resulting in radiculopathy, paresis, and paralysis - Pulmonary embolism - Hemothorax or pneumothorax - Infection - Unintended puncture - Hemorrhage - Hematoma
Design of the clinical investigation	
Clinical development stage	
Pivotal confirmatory.
 
Justification: pre-market study for demonstration of conformity of the device with the Essential Requirements for CE-marking.

Design type	Prospective, Single arm, Multicenter
Control group	No control group
Comparator (control device or treatment)	No comparator, on the other hand the clinical outcomes of this palliative treatment will be compared with the clinical data obtained with similar devices in similar clinical conditions.
Measures to minimize/avoid bias	
 - New technology bias is minimized through an adequate training to the Medical Operator - Low statistical bias is minimized through an adequate estimate of the number of patients in the treatment group as compared to the state of the art - Multicentric study to minimize usability bias
Primary endpoint(s)	
 - Change of Worst Pain Score expressed as average reduction of 2 BPI (Brief Pain Inventory) scores: Thoracic/Lumbar/ Peri-acetabulum/Iliac Crest/Sacrum RF Ablation [Time Frame: Baseline, 3 months]. 
Change in pain will be calculated as:
 $\mu c = \text{worst-pain 3-month} - \text{worst-pain baseline}$ 
A negative average value for change in pain represents a lowering of the subject's pain score (an improvement, or reduction in pain) and a positive value represents an increase in the subject's pain score (a worsening or increase in pain).
 
Worst pain score at the target treatment site will be collected from the BPI in the past 24 hours.
 
 - Completion (%) of the ablation procedure without device-related adverse events including in particular nerve injury [Timeframe: Post-procedure, 3 months]. 
All the analyses will be performed according to ITT and PPT principle.

Secondary endpoint(s)	
 - Change of Worst Pain Score: Thoracic/Lumbar/ Peri-acetabulum/Iliac Crest/Sacrum RF Ablation [Time Frame: 1 month, 12 months]. Worst pain score at the target treatment site will be collected at each timepoint from the Brief Pain Inventory (BPI) in the past 24 hours. - Usability endpoint: Technical success (ability to perform access to treatment site and perform ablation) and procedural success (ability to perform access to treatment site and perform ablation for one or more complete cycles as planned by the physician) without product specialist intervention [Timeframe: Post-procedure]; - Procedural endpoint: procedure time, number of procedural errors, number of procedural and technical success for the same surgeon [Time Frame: Post-procedure]; 
All analyses will be performed according to ITT and PPT principle.

Sample Size	52 subjects in a maximum of 10 sites
Follow-up	Baseline, Intra Procedure, Post procedure (within 24 hours), 1 month, 3 months and 12 months.
Duration of the clinical investigation	
Upon obtaining informed consent, each subject will complete an Enrollment/Baseline visit, SPINERY procedure visit (Day 0), prior to discharge (within 24 hours), 1 month and 3 months clinic visits), and a final post-procedure study visit (12 months) for a total of 5 study related visits.
 
The estimated time needed to enroll all subjects is approximately 6 months. The estimated time needed to obtain the CE Mark due to safe endpoints is 9 months (6 months for enrollment plus 3 months follow-up).
 
The overall study duration, from first subject enrollment to last subject visit (including 12-month follow-up), is expected to last approximately 18 months. The completion of the study is defined as the approval of the Final Study Report and closure of all sites.

Inclusion criteria	
 1. Patients with painful metastatic malignant lesions involving bone; 2. Patients, candidates to standard therapy, in which the RF ablation can be performed in combination with the Standard Therapy in accordance with the Investigator's indications; 3. Patients who have failed, not candidates or refuse Standard Therapy (chemotherapy or radiotherapy); 4. Patients with metastatic tumor size compatible with the expected ablation dimensions as reported for SPINERY devices in the IFU;

	
 5. Patients with localized pain resulting from not more than two sites of symptomatic metastatic disease 6. Patients that do not have evidence of impending fracture 7. Patients with metastatic lesions targeted for treatment located in the thoracic and/or lumbar vertebral body(ies), peri-acetabulum, iliac crest, and/or sacrum - no restrictions on location of lesion; 8. Patients with BPI-Report worst pain score $\geq 4/10$ at the target treatment site within the past 24 hours 9. Patients with Karnofsky score ≥ 40 at enrollment 10. Patients willing and able to provide a signed and dated informed consent, comply with the study plan, follow up visits and phone calls 11. Patients at least 18 years old at the time of informed consent
Exclusion criteria	
 12. Patients implanted with heart pacemaker or other implanted electronic device 13. Patients with previous mechanical bone stabilization in the vertebral body to be treated 14. Use of SPINERY in vertebral body levels C1-C7 15. Multiple myeloma, solitary plasmacytoma, or primary malignant lesions in the index vertebra or bone. 16. Active or incompletely treated local infection at the planned treatment site(s) and/or systemic infection. 17. Planned treatment site(s) accompanied by objective evidence of secondary radiculopathy or neurologic compromise. 18. Planned treatment site(s) associated with spinal cord compression or canal compromise requiring decompression. 19. Fractures due to prostatic cancer or other osteoblastic metastases to the spine. Metastatic lesions originating in the prostate that are osteolytic or of mixed origin are eligible for the study. 20. Pregnant, breastfeeding, or plan to become pregnant during the study duration. 21. Concurrent participation in another clinical study that may add additional safety risks and/or confound study results. 22. Any condition that would interfere with the subject's ability to comply with study instructions or might confound the study interpretation.

Table A - Schedule of Visits

	Enrollment Baseline	SPINERY Procedure (Day 0) ²	Post- Procedure (within 24 hours)	1-Month Follow-up (±7 days)	3-Months Follow-up (±10 days)	12-Months Follow-up (±30 days)
Informed Consent Form ¹	X					
Inclusion/Exclusion Criteria	X					
Medical History with Demographics	X					
Physical Examination	X		X		X	
Karnofsky Performance Scale	X					
PI assessment of local tumor control (optional)		X		X	X	X
Concomitant pain medications	X	X	X	X	X	X
BPI (Short Form) – includes worst pain score in the past 24 hours	X			X	X	X
EQ-5D-5L ³	X			X	X	X
Adverse Events Assessment	X	X	X	X	X	X
Deviations	X	X	X	X	X	X
Usability Assessment		X				
Tumoral lesion compatibility (clinical estimate)	X	X				

1) Informed consent must be obtained prior to performing any study-specific procedures.
 2) Baseline Visit, Enrollment Visit and procedure can occur on the same day.
 3) EQ-5D-5L is a standardized instrument for measuring generic health status

2. CLINICAL BACKGROUND AND RATIONALE

Painful bone metastases are a common cause of morbidity in patients with metastatic cancer, especially when combined with possible neural compression and pathologic fractures. Several solid cancers are associated with bone involvement, most often, prostate and breast, with 30% to 70% of cancer patients who develop bone metastases [1]. The skeletal system is the third most common site for cancer metastases, surpassed only by the lungs and liver. Many tumors, especially those of the breast, prostate, lungs, and kidneys, have a strong predilection to metastasize to bone, which causes pain, hypercalcemia, pathological skeletal fractures, compression of the spinal cord or other nervous structures, decreased mobility, and increased mortality. Metastatic cancer-induced bone pain is a type of chronic pain with unique and complex pathophysiology characterized by nociceptive and neuropathic components [2].

Falk et al. have studied the physiopathology of the cancer pain and especially the one caused by metastasis to bone, is a severe type of pain, and unless the cause and consequences can be resolved, the pain will become chronic. As detection and survival among patients with cancer have improved, pain has become an increasing challenge, because traditional therapies are often only partially effective. Until recently, knowledge of cancer pain mechanisms was poor compared with understanding of neuropathic and inflammatory pain states. Cancer-induced bone pain is a mixed-mechanism pain state exhibiting elements of both neuropathic and inflammatory pain, but with distinctive modifications to the tissue and nerves in the periphery as well as unique neurochemical changes at the spinal cord level. Thus, it is a complex syndrome involving inflammatory, neuropathic, ischemic, and cancer-specific mechanisms, often occurring at more than one site. Inflammatory infiltration occurs as a result of direct tissue damage caused by tumor growth as well as release of pain mediators by the cancer cells. The neuropathic component of the pain can result from cancer-induced damage to the sensory nerves caused by infiltration and/or compression by the tumor cells, tumor-induced hyperinnervation and stretching or denervation as the bone expands and degrades. In addition, neuropathy can arise as a subsequent consequence of therapeutic intervention, such as chemotherapy or surgery [3].

In the recent years many studies have been conducted to evaluate the efficacy of palliative pain treatments. Filippiadis et al. sustain that imaging-guided percutaneous techniques may act either indirectly or directly to provide significant pain alleviation and life quality improvement. Palliative treatment options include neurolysis, thermal ablation, bone consolidation, and high- intensity-focused ultrasound. Technical advantages of these procedures include the minimally invasive nature that can be performed in the outpatient setting or with a short hospitalization, low complication rates, little to no interruption of systemic chemotherapy agents, and ability to combine with other palliative treatment options [4].

A number of different methods have been proposed for pain relief in cancer patients with bone metastases, including systemic analgesics, bisphosphonates, antitumor chemotherapy, radiotherapy, systemic radio-isotopes, local surgery and vertebroplasty [1,7,8], each one presenting with different indications, contraindications and complications.

Percutaneous, image-guided, "*in situ*" tumor ablation with a thermal energy source, such as a Radio-Frequency (RF), Laser or Microwave source, have been investigated for decades as an effective and minimally invasive approach in patients with a variety of primary and secondary malignant neoplasms, including tumors located

[figure not shown]
in the brain, musculoskeletal system, thyroid and parathyroid glands, pancreas, kidney, lung, liver, and breast [7]. This “*in-situ*” technique permits the destruction of tumors without necessitating their removal and in many cases can be used in place of more invasive and expensive surgical techniques. Moreover, the procedure can be performed in an outpatient setting, and gives a chance of treatment to patients who would not otherwise be considered candidates for surgery due to age, comorbidity, or extent of the disease [7].

Percutaneous radiofrequency (RF) ablation is an emerging, minimally invasive therapy for patients with metastatic bone disease who have not responded or have contraindications to radiotherapy [9]. The ablation probe, consisting of straight or expandable electrodes, is placed into the body through a sub-centimeter incision and directed into the tumor using imaging guidance. The electrodes deliver a high-frequency (375–500 kHz) alternating current into the lesion, which produces agitation of tissue ionic molecules that causes frictional heating (hyperthermia). Local tissue temperatures reach 60–100°C, causing protein denaturation and coagulative necrosis of the tumor.

The devitalization of tissues leads to a lowering of perceived pain both directly through the destruction of periosteal nociceptors and indirectly by reducing tumor bulk. In fact, the proposed mechanisms by which RF ablation decreases pain may involve pain transmission inhibition by destruction of sensory nerve fibers in the periosteum and bone cortex; reduction of lesion volume with decreased stimulation of sensory nerve fibers; destruction of tumor cells that are producing nerve-stimulating cytokines (tumor necrosis factor-alpha [TNF- α], interleukins, etc.) and inhibition of osteoclast activity [10,11,12].

The pain control in oncology is an important clinical element interconnected with the adopted therapy as stated in the ESMO and NCCN Guidelines. Increasing evidence in oncology are showing that survival is linked to symptom control and that pain management contributes to broad quality-of-life improvement. To maximize patient outcomes, pain management is an essential part of oncologic management [5,13].

Bagla et al. [14] in their clinical study treated 50 patients and performed RF ablation in thoracic and lumbar vertebral bodies. FACT-BP (Quality of Life test) improved from 22.6 to 38.9 ($p < 0.001$). No complications related to the procedure were reported. In conclusion the RF ablation with cement augmentation safely and effectively reduces pain and disability rapidly, while increasing quality of life in patients suffering from vertebral body metastases.

According to preliminary results by Dupuy et al. [15], RF ablation can provide palliative treatment for patients with painful osseous metastases. Later on, Callstrom et al. [16] reported positive results in the treatment of 12 patients with severe pain, related to osteolytic metastasis, in whom RT or chemotherapy had previously failed, concluding that RF ablation provides an effective and safe alternative method of pain palliation in patients with osteolytic metastases. A multicenter clinical study involving 43 patients with painful osseous metastases showed again significant reduction of pain and decrease in the use of opioids, with only minor complications

[figure not shown]
in patients with bone metastases who failed standard treatments [17]. Finally, CT-guided RF ablation proved to be effective for the treatment of painful bone metastases in a group of 30 patients. After treatment the authors observed a significant decrease, in the mean past-24-h, of Brief Pain Inventory (BPI) score for worst pain, average pain and pain interference during daily life (4.7, 4.8 and 5.3 units respectively) and a marked decrease (3 out of 30 patients at 4 and 8 weeks after treatment) in use of analgesics [9].

More recently Tomasian et al. [18] stated that in accordance with the latest NCCN Guidelines for adult cancer pain (version. 2019), thermal ablation may be considered for palliation of metastatic bone pain in the absence of an oncologic emergency when chemotherapy is inadequate and radiation therapy is contraindicated or not desired by the patient.

Many spinal tumors will continue to grow and cause pain after radiation therapy. Posterior vertebral body tumors will often progress and extend through the posterior cortex into the spinal canal, despite radiation therapy. As reported by Hillen et al. [18] RF ablation, in addition inducing pain relief, can often stop further progression of the posterior tumor extension and this RF technique does not hinder or delay the use of adjuvant therapies such as radiation therapy and may provide an alternative therapy for tumors not controlled with systematic chemotherapy or radiation therapy.

Other important works show the efficacy of RF even before RT. The study of Janjan [20] demonstrate that RT is active usually not before 6-8 weeks as analgesic and 10-12 weeks to recalcification. The author concludes saying that the treatment of painful metastases, the ablative treatment should be always performed before the RT because the analgesic effect of RF ablation is immediate compared to radiotherapy, whose undoubtedly effectiveness is usually obtained in the medium to long-term.

The same clinical evidences were observed by Di Staso [21] where 15 patients, treated with RF ablation followed by RT, were compared with a matched group (30 subjects) only treated by RT. Response at 12 weeks documented a pain relief in 53.3% and 16.6% of the subjects treated by RF-RT or RT respectively. The overall response rate at 12 weeks in pain relief was 93.3% in the group treated by RF-RT and 59.9% in the group treated by RT alone. Although recurrent pain was documented more frequently after RT (26.6%) than after RF-RT (6.7%) the results suggest that RF ablation before RT treatment is safe and more effective in pain reduction than RT alone.

In conclusion of this clinical literature review several aspects can be outlined in support to the role of RF ablation of metastatic tumors in bones with the aim to obtain a palliative pain reduction in patients:

1. The metastatic tumors of the vertebral bodies are very painful for the patients;
2. The RF ablation has been found to be effective, thanks to its local hyperthermia, destroying the sensory nerve fibers in the periosteum and bone cortex (direct effect);

3. The RF ablation has also an indirect effect expressed by the local reduction of the metastatic lesion reducing the stimulation of the sensory nerves;
4. The palliation of pain, obtained with RF ablation, is associated with a quick decrease in assumption of opioids and similar drugs for pain control;
5. The pain relief obtained by RF ablation is higher and pain is less recurrent than that one obtained with RT;
6. The RF ablation is also effective for the treatment of posterior vertebral body tumor expansion when standard therapy is not completely effective;
7. The RF ablation is clinically indicated for the pain relief in patients when the Standard Therapy fails, when it is contraindicated or when it is refused by the patient;
8. The RF ablation is clinically indicated in addition to RT since it promotes a faster pain symptoms relief without compromising the application of the Standard Therapy.

SPINERY is a Radio-Frequency (RF) device designed for local treatments of metastatic bone tumors.

The Intended Purpose is:

SPINERY is a Radiofrequency (RF) device designed for palliative treatment of patients with painful metastatic bone tumors involving vertebral bodies, sacrum, iliac crest and peri-acetabulum.

The SPINERY Intended Clinical Performance is:

- Pain reduction in patients affected by metastatic bone tumors involving the vertebral bodies, sacrum, iliac crest and peri-acetabulum, in patients with indication for Standard Therapy and in patients who have failed, not candidates or refuse Standard Therapy;
- Coagulation and ablation of bone tissue during interventional procedures including palliation of pain associated with metastatic lesions involving bone also in patients with indication for Standard Therapy who have failed, not candidates or refuse Standard Therapy.

The device is conceived to treat bone metastatic tumor areas using RF needles, with the aim of pain reduction. The RF needles are used single or in combinations to increase ablation efficacy. The SPINERY system consists in a RF generator connected to a handle carrying on a 16G needle. The RF needles are bipolar or monopolar with cooling and equipped with two thermocouples (one distal to measure the center ablation temperature and one proximal to avoid hyperthermic damages to the healthy tissues. The procedure is conducted under Fluoroscopy imaging guidance.

The peculiarity of this device is that, thanks to the availability of several accessories (electrodes), it provides physicians with the ability to plan the ablation volume in terms of shape and design a personalized shape and volume of the ablated area. This allows for a more individualized treatment, since a personalization of ablation area shape is not possible in the state of art technology, which allows only spherical ablation.

While the safety of the device is completely described thanks to compliance to international standards (safety tests reports and General Safety and Performance Requirements checklist are available as Annexes of Technical File on file at Axon), its clinical benefit needs further investigation on human subjects as the device is not completely equivalent to any other currently available on the market.

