4.1. Primary Objectives

- To demonstrate that SPINERY RF device is effective in short-term (3 months) pain reduction in patients affected by metastatic bone tumors involving the vertebral bodies, sacrum, iliac crest and peri-acetabulum with indications for standard therapy in patients who have failed, not candidates or refuse standard therapy;
- To demonstrate that SPINERY RF device is safe in the RF ablation treatment of metastatic bone tumors, without causing device-related adverse events including in particular nerve injury;

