6.3.1. Inclusion criteria

Participants are eligible to enroll in the study only if *all* the following criteria apply:

1. Patients with painful metastatic malignant lesions involving bone;
2. Patients, candidates to standard therapy, in which the RF ablation can be performed in combination with the Standard Therapy in accordance with the Investigator's indications;
3. Patients who have failed, not candidates or refuse Standard Therapy (chemotherapy or radiotherapy);
4. Patients with metastatic tumor size compatible with the expected ablation dimensions as reported for SPINERY devices in the IFU;
5. Patients with localized pain resulting from not more than two sites of symptomatic metastatic disease;
6. Patients that do not have evidence of impending fracture;
7. Patients with metastatic lesions targeted for treatment located in the thoracic and/or lumbar vertebral body(ies), peri-acetabulum, iliac crest, and/or sacrum - no restrictions on location of lesion;
8. Patients with BPI-Report worst pain score $\geq 4/10$ at the target treatment site within the past 24 hours;
9. Patients with Karnofsky score ≥ 40 at enrollment;
10. Patients willing and able to provide a signed and dated informed consent, comply with the study plan, follow up visits and phone calls;
11. Patients at least 18 years old at the time of informed consent.

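### The pooled 3-month pain change mixes ablation with radiotherapy in patients irradiated around Day 0, so rejecting zero does not by itself show that SPINERY is effective

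*Combined protocol and SAP*

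**What the plan says.** - **Objective (section 4.1).** "To demonstrate that SPINERY RF device is effective in short-term (3 months) pain reduction". Section 6.1 ties the 3-month report to the CE mark.
- **Hypothesis (Synopsis).** The null value is zero, and the tested parameter "is the mean change from baseline to the 3-month visit in worst-pain score". The visit window is ±10 days. There is no control group. The Synopsis mentions a comparison with data from similar devices but gives no figure or method.
- **Population (section 6.3.1).** Criterion 2 admits patients who are "candidates to standard therapy, in which the RF ablation can be performed in combination with the Standard Therapy". Criterion 3 covers those for whom standard therapy failed, is unsuitable or is refused, and identifies that therapy as chemotherapy or radiotherapy. Neither 6.3.1 nor 6.3.2 states an interval since the last radiotherapy.
- **Background (section 2).** Radiotherapy is said to be "demonstrate that RT is active usually not before 6-8 weeks as analgesic and 10-12 weeks to recalcification" in the first source's account, whereas ablation is described as immediate. A matched comparison is then reported: "The overall response rate at 12 weeks in pain relief was 93.3% in the group treated by RF-RT and 59.9% in the group treated by" radiotherapy alone.
- **Recording (sections 6.4.4 and 7.3).** Pain, osteoporosis and steroid medicines are updated at each visit. Radiotherapy is not listed. Relevant cancer history is taken at baseline, without any stated need for radiotherapy dates or target lesion.
- **Analysis (sections 10.1 to 10.4).** ITT first, per-protocol second, with BPI change at 1, 3 and 12 months. There is no stratum, covariate, intercurrent-event rule or sensitivity analysis for radiotherapy.

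**The concern.** A single-arm test against zero asks whether pain fell, not why. That is a tolerable basis for a device claim only if little else would be expected to lower pain over the same period. Here the protocol itself names a second treatment that lowers pain, allows it alongside ablation, and gives it a delay that has elapsed by the primary visit. For patients irradiated around Day 0, the endpoint is the sum of two effects, and nothing in the plan allows them to be separated afterwards. At stake is the main efficacy sentence of the CE-mark report: a significant pooled result could be read as proof for SPINERY when part of it, or in the extreme all of it, came from radiotherapy.

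Prior radiotherapy is a possible further source. With no stated interval since the last course, a delayed response to an earlier course could also fall within follow-up.

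**Working it through.** **1. Reproduce the plan's sample size.** Inputs from section 10.2: SD 3, correlation 0.3, difference 2, two-sided alpha 0.05, power 0.90.

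- SD of change = 3 × √(2 × (1 − 0.3)) = 3.55.
- Paired t-test (noncentral t): power is 0.899 at n = 35 and 0.908 at n = 36, so 36 is confirmed.
- 36 / (1 − 0.30) = 51.4, rounded up to 52, also confirmed.
- SE of the mean change at n = 36: 3.55 / 6 = 0.59. The smallest significant mean change is 2.03 × 0.59 = 1.2 points.

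**2. Compare the visits with the stated onset** (taking a month as 30 days).

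- 3-month visit: 90 ± 10 = 80 to 100 days, or 11.4 to 14.3 weeks. This is past 6 to 8 weeks for radiotherapy given at Day 0. Even at the earliest permitted visit it is past onset for radiotherapy started up to 11.4 − 8 = 3.4 weeks after ablation (8-week onset) or 11.4 − 6 = 5.4 weeks (6-week onset).
- 1-month visit: at most 30 + 7 = 37 days, before 6 weeks (42 days). This holds only for radiotherapy starting at or after Day 0.

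**3. Probability of rejecting zero if SPINERY adds nothing.** Taken from section 2: 59.9% respond at 12 weeks with radiotherapy alone. Assumed, because the documents do not say: the share irradiated, a fall of 2 or 3 points per responder, and 0 in everyone else.

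Mean fall = share × 0.599 × points. Noncentrality = mean fall / 0.59, with 35 df and two-sided 0.05.

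| Share irradiated | Mean fall, 2 points | P(reject zero) | Mean fall, 3 points | P(reject zero) |
|---|---|---|---|---|
| All | 1.20 | 50% | 1.80 | 84% |
| Half | 0.60 | 17% | 0.90 | 31% |
| A quarter | 0.30 | 8% | 0.45 | 11% |

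The nominal level is 5%. Adding the variance from mixing responders and non-responders, p(1 − p) × points² with p = share × 0.599, lowers these a little: to 47%, 16% and 8% at 2 points, and to 78%, 28% and 11% at 3.

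**4. The same scenarios against a 2-point mark.** Section 5.1 describes the endpoint as an average reduction of 2 points. The chance of an observed mean fall of at least 2 is 1 − Φ((2 − mean fall) / 0.59).

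- At 2 points per responder: about 9%, 0.9% and 0.2% for all, half and a quarter irradiated.
- At 3 points per responder: about 37%, 3% and 0.4%.

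**5. Precision without radiotherapy.** If 18 such patients complete (an assumption), the 95% half-width is 2.11 × 3.55 / √18 = 1.8 points, against 1.2 for 36. Power for 2 points is 62%, against 91%.

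**The case against.** The strongest reply is that combined use is intended. The objectives include patients with an indication for standard therapy, so a pooled result describes the population in which the device would be used. That stands, and it is why those patients and the pooled analysis should stay. It does not support a conclusion worded as the effect of SPINERY.

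Second, the inflation may be small. With a quarter irradiated it is 8% to 11% against 5%, and if success meant a 2-point mean fall, an inert device would seldom pass under the 2-point assumption. Both are correct. But the share is unknown, and the only formal hypothesis in the Synopsis is against zero.

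Third, the cited comparison favours combined treatment over radiotherapy alone, 93.3% against 59.9%. That rests on a matched group, which this trial lacks. The 59.9% comes from 30 patients, response is not defined there in BPI points, and recurrent pain was reported in 26.6% after radiotherapy, so the conversion to points is only illustrative.

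Fourth, exclusion 22 bars conditions that could confound interpretation, and section 6.5.2 allows withdrawal when progression needs other treatment. These are partial safeguards. Neither addresses planned radiotherapy, which criterion 2 allows.

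A reader might also infer that radiotherapy is at its strongest at 3 months, or that recently irradiated patients are knowingly admitted as failures. The documents support neither. Section 2 gives an analgesic onset, and its 10 to 12 weeks refers to recalcification. No text expressly admits patients soon after radiotherapy; the plan is simply silent on the interval.

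**Conclusion.** The point holds for the pooled mean. In patients irradiated around Day 0, the 3-month change combines ablation and radiotherapy, the plan does not separate them, and rejecting zero does not by itself show that SPINERY is effective. With an inert device, the chance of rejecting zero runs from 8% (a quarter irradiated, 2 points per responder) to 84% (all irradiated, 3 points). These figures rest on the plan's SD and correlation, 36 completers, the cited 59.9%, and assumed values for the share irradiated and the size of response.

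A reader might go further and conclude that none of the 3-month change can be credited to SPINERY. The documents do not support that: patients who receive no radiotherapy are not confounded by it, and the number irradiated is not given. The carry-over from earlier courses is a possibility arising from an unstated interval, not something the plan provides for.

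**What to change.** 1. **Record.** Enter in the eCRF the dates of radiotherapy to the target lesion, before and during the study.
2. **Word the pooled claim.** Keep the pooled primary analysis in section 10, but state its conclusion as the change after SPINERY with or without standard therapy.
3. **Pre-specify groups fixed at baseline.** Report the 3-month change with 95% CI for radiotherapy to the target lesion given within 12 weeks before Day 0 or planned at Day 0, against neither. Treat unplanned radiotherapy after Day 0 as an intercurrent event in a sensitivity analysis, for example counted as no improvement. Do not move patients between groups on it: that would remove those whose pain returned and flatter the device.
4. **Name the supportive result.** For patients whose radiotherapy starts at or after Day 0, designate the 1-month change, which precedes the stated onset.
5. **Limit the claim for SPINERY alone.** Draw it only from the no-radiotherapy group, as an estimate with its interval. Chemotherapy, cementoplasty (section 7.1) and unrestricted medication (section 7.3) may still contribute there and should be acknowledged.
6. **Reconcile the population.** Criteria 2 and 3 both sit in a list where all must apply, and section 4.1 drops the conjunction that the Synopsis places between the two populations. The sponsor must make these agree.

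The cost is wording in section 10 and a few eCRF fields, with no extra patients or visits. The downside is precision: with 18 completers in the no-radiotherapy group, about ±1.8 points and 62% power for 2 points.
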